### **Body height and derived parameters**

Patients' body height is determined at each visit. The three other primary endpoints are calculated using the recorded height measurements. HV will be calculated in cm/year as the difference between two height measurements divided by the time interval (in days) between these two measurements and multiplied by 365.25. Patients' body height at start of treatment serves as baseline value for calculating HV at month 3, 6, 9 and 12. From the 15-months-visit onwards, the baseline value for HV calculation will be patients' body height at the visit dating back 12 month in the past, e.g., height after 3 months will serve as baseline value to determine HV at 15-months-visit, height after 6 months will serve as baseline to determine HV at 18-months-visit, and so on ("moving 12-months HV basis").

HV and HV SDS for the baseline visit are calculated using historical height data. All corresponding values are recorded in the CRF. The historical reference values to assess the height velocity at screening (V0) and baseline (V1) will be assessed as follows: The historical value, which was assessed next to day 365 prior to height assessment at baseline, will be selected. If there are two values, one assessed x days prior to day 365 and one assessed x days after day 365, the one assessed longer ago will be selected. Derived height velocity values will be rounded to two digits. If for any historical height assessments, the assessment date was given partial only, the 15th of the respective month will be used. If in the final data negative HV values are assessed, this will be set to 0 for analysis.

Height and height velocity will also be expressed in SDS. SDS reflects the deviation of a measured value from the mean value of normally growing children of the same sex and chronological age, expressed in units of the standard deviation of normally growing children of the same sex and chronological age.

In general, the SDS values for H and HV will be calculated according to the formula  $SDS = (X1 - X2)/SD$ , where X1 is the measured value, X2 the mean value for the relevant chronological age and sex, and SD the standard deviation for the relevant sex and age. Standardization of patients' height will be performed according to the protocol using national reference ranges of body height (Appendix B). If respective national references for height are provided as median and 3rd percentiles SDS values will be calculated according to the following formula:  $SDS = (X1 - X3) / (0.5 * (X3 - X4))$ , where X1 means the measured value, X3 the median value for the relevant chronological age and sex, and X4 the 3rd percentile for the relevant chronological age and sex applying the respective national references. Resulting SDS values will be rounded to two digits.

To derive reference values for age groups in between the age groups reported in literature, the original tables were extended by linear interpolation between the reported values for mean and standard deviation. Standardization of a patient's HV between two successive visits will be based not on the patient's chronological age at the time of the second of the two visits, but on the mean of the chronological ages at the two visits. Means and standard deviations of normally growing children will be taken from tables provided by Prader (1989). To derive reference values for age groups in between the age groups reported by Prader (1989), the original tables

were extended by linear interpolation between the reported values for mean and standard deviation (Appendix A). To derive references values for patients older than the provided age groups the reference for the maximal age will be used (for H and HV).

In order to derive individual HV SDS values, two methods of HV standardization will be used. The two alternative methods used for standardization:

- cross sectional = HV SDSCS,
- peak centered, HV SDSPC,

differ only regarding the reference tables used to look up values for means and standard deviations (reference values) for the standardization.

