### **4        Study design**

This study is designed as a phase IV, prospective, open label, non-comparative, multicentre trial. Safety and efficacy will be assessed periodically during treatment.

Treatment should be discontinued after the first year of treatment if the height velocity SDS is below +1. Treatment will continue until final height (height velocity < 2 cm/year, [REDACTED]

[REDACTED] is reached but will be discontinued earlier if medically indicated or if there is inadequate response to treatment.

A summary of the study plan is given below.

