### **10.5 Analysis of efficacy endpoints**

#### **10.5.1 Auxological endpoints**

These are height, height SDS, height velocity and height velocity SDS. These parameters will be monitored at baseline, at every 3 months during GH treatment and at the end of treatment. The effectiveness of treatment in inducing growth will be determined by descriptive statistics of the height at each scheduled visit including a comparison to the height at baseline. Similar analyses will be conducted for the height SDS.

The effectiveness of treatment in accelerating linear growth rate will be determined by analyzing the annual height velocity in cm/year (the difference between two height measurements divided by the time interval between these two measurements multiplied by 365.25) at each scheduled visit and by comparing it to the height velocity determined at baseline using historical data. Similar analyses will be conducted for the height velocity SDS.

Treatment will be considered to be ineffective (leading to drug discontinuation) if HVSDS remains below +1 in the first year of treatment.

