## 4.6 Analysis of secondary endpoints

### 4.6.1 Efficacy evaluation

Data regarding efficacy endpoints will be summarized by visit. Time trends of means will be presented graphically for the secondary endpoints.

For all endpoints, 95% confidence intervals will be calculated for the mean difference between the baseline visit and all later visits, respectively.

Summary tables, plots, and confidence intervals will be presented by visit for the FAS analysis set as well as by sex and the two Omnitrope formulations (i.e. initially treatment). All summary table stratified by initially treatment will be limited to the visit during the first year of treatment. Plots presenting parameters in SDS will not be presented by sex. No plots by initially treatment will be presented. In summary tables presenting data that is also presented graphically confidence limit for means will be added.

All efficacy analyses will be done by completers (who reached the final height) and total.

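### Setting negative height velocities to 0 biases late-visit mean HV upwards, probably by a small amount, and this floor is neither in the protocol formula nor in the SAP's list of changes

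*SAP*

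**What the plan says.** The SAP defines HV as a plain difference, annualised with a year of 365.25 days: "HV will be calculated in cm/year as the difference between two height measurements divided by the time interval (in days) between these two measurements". From the 15-month visit onwards the "baseline value for HV calculation will be patients' body height at the visit dating back 12 month in the past". After the text on historical heights, the same section adds: "If in the final data negative HV values are assessed, this will be set to 0 for analysis". It gives no exception, no rationale, no unfloored analysis and no count of altered values.

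The protocol (sections 7.3.3 and 10.5.1) uses the same formula without a floor: "the difference between two height measurements divided by the time interval between these two measurements multiplied by 365.25". SAP section 3 lists three changes to the planned analyses: the WHO diabetes criteria, the compliance assessment and the anti-HCP analysis. The floor is not among them.

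HV and HV SDS are reported as visit means with confidence limits, for completers and for all patients. They are also reported as changes from baseline, for which "95% confidence intervals will be calculated for the mean difference between the baseline visit and all later visits, respectively". Late visits approach low velocities by design: "Treatment will continue until final height (height velocity < 2 cm/year" (Protocol section 4; the rest of that definition is redacted).

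**The concern.** A small negative HV in a child who has almost stopped growing is usually measurement error around a true value close to zero. Equally large positive errors are just as wrong, but they are kept. In a mean the two sides would largely cancel. Once one side is replaced by 0, they no longer do.

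At stake are the late-visit means of HV, their confidence intervals, and possibly HV SDS, mostly in the completer rows. The table shells would not reveal the problem, because a floored minimum prints as 0 and no column shows how many values were changed.

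**Working it through.** The plan states no figure that depends on the floor, so there is nothing of its own to reproduce.

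**Direction.** Since max(x, 0) ≥ x, a single negative value is enough to raise the mean. For any two values, |max(x, 0) − max(y, 0)| ≤ |x − y|, so the sample SD, and with it the width of the CI for mean HV, cannot increase. Example: −0.4, 0.0, 0.6, 1.2, 1.8 has mean 0.64 and SD 0.89. After flooring the mean is 0.72 and the SD 0.78.

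**Inputs.** The documents give neither a height measurement error nor a late-visit HV distribution. I assume HV ~ N(μ, s²). For scale, an assumed error SD of 0.2 to 0.5 cm per height gives a 12-month difference with SD √2 × 0.2 = 0.28 to √2 × 0.5 = 0.71 cm.

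**Formulas.**
- Bias = E[max(X, 0)] − μ = s·φ(μ/s) − μ·Φ(−μ/s)
- E[max(X, 0)²] = (μ² + s²)·Φ(μ/s) + μ·s·φ(μ/s)

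For μ = s = 0.5, the bias is 0.5 × 0.2420 − 0.5 × 0.1587 = +0.042 cm/year. The second moment is 0.5 × 0.8413 + 0.25 × 0.2420 = 0.4812. The SD is √(0.4812 − 0.5417²) = 0.433, a ratio of 0.433/0.5 = 0.87.

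| Assumed mean | Assumed SD | Negative values | Bias (cm/year) | CI width ratio, mean HV | Simulated 95% CI coverage, n = 150 |
|---|---|---|---|---|---|
| 0.5 | 0.5 | 15.9% | +0.042 | 0.87 | 0.80 |
| 1.0 | 0.7 | 7.7% | +0.024 | 0.93 | 0.93 |
| 1.0 | 1.0 | 15.9% | +0.083 | 0.87 | 0.81 |
| 1.5 | 0.7 | 1.6% | +0.004 | 0.99 | 0.95 |

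The n of 150 is also assumed. At n = 50 the first row has coverage 0.91. Without the floor, bias is 0 and coverage is 0.95 throughout.

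**Range.** These four rows do not bound every combination. Mean 1.5 with SD 0.5 gives +0.0002. Mean 0.5 with SD 1.0 gives +0.198 and ratio 0.74, but needs 31% negative values. Over means of 0.25 to 2 and SDs of 0.3 to 1.0, bias runs from 0.00 to +0.29 and the ratio from 1.00 down to 0.67. The extreme (0.25, 1.0) needs 40% negatives.

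**Earlier visits (assumed).** Mean 5, SD 1.5 gives +0.0002. Mean 9, SD 3 gives +0.001.

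**HV SDS.** The score is (X1 − X2)/SD, "where X1 is the measured value, X2 the mean value for the relevant chronological age and sex". If the floored HV enters as X1, the bias is the HV bias divided by the reference SD: 0.0417/0.5 = +0.083 SDS for an assumed reference SD of 0.5. For patients older than the tables, "the reference for the maximal age will be used (for H and HV", so the divisor is whatever SD stands at that age. The tables are not printed. With mixed age references, the simulated SD ratio was 0.87 to 1.00.

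**Change from baseline.** The variance of the difference also depends on the covariance with baseline HV, which flooring reduces. With an assumed baseline mean of 5 and SD of 1.0 or 1.5, and late-visit (mean, SD) pairs (0.5, 0.5), (1, 0.7), (1, 1) and (0.25, 0.5), the width ratio is 0.94 to 0.99 at correlation 0, 0.96 to 1.06 at correlation 0.6, and 1.05 to 1.21 at correlation 0.9.

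**The case against.** The best defence is that true height loss is implausible, so 0 is a sensible bound. If true HV is 0 or more, flooring never moves a patient's value further from the truth. That stands for individual values. It does not rescue a mean, where the errors would otherwise cancel.

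Several limits on scope also stand:

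- **Size.** A reader might infer a bias of up to +0.28 cm/year and an interval 42% too narrow. With true HV 0 and measurement error as the only variation, the formulas do give 0.399 × 0.71 = +0.28 and an SD ratio of 0.584. The SAP, however, tabulates by scheduled visit and assigns final visits to scheduled ones, so visit means mix growth stages. As an illustration, an error SD of 0.28 to 0.71 gives a bias of +0.004 to +0.10 at true HV 0.5. If 30% of a visit's patients are at that level and the rest at 2 or more, the visit bias is about +0.001 to +0.03.
- **Intervals in general.** A reader might infer that all planned intervals narrow. That is guaranteed only for mean HV. The change-from-baseline interval can go either way.
- **Favouring treatment.** A reader might infer that the rule flatters the product. The study is single-arm and descriptive. The sentence also follows the text on historical HV, and flooring a negative baseline value would lower the change.
- **HV SDS.** The SAP calls X1 the measured value, so whether the floored HV is standardised is left open.
- **Data cleaning.** The reference to final data suggests that the rule applies after cleaning. Cleaning removes gross errors, but ordinary measurement error around zero remains.

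**Conclusion.** The point holds as a minor one. The upward direction for mean HV is certain once one negative value occurs, and the CI of mean HV can then only stay equal or narrow. The size rests on assumed late-visit distributions. Hundredths of a cm/year is the likely order, and larger values need a third or more of a visit's patients to have negative HV, which I think unlikely but cannot exclude from the documents. The conclusion extends to HV SDS only if the floored value is standardised. Height, height SDS and the primary diabetes endpoint are untouched. The floor is also an undeclared departure from the protocol formula, whatever its size.

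**What to change.** Delete the sentence from SAP 4.6.1 and analyse HV and HV SDS as calculated, negative values included, at baseline and at all later visits. Report the number of negative HV values per visit. If the floored version is wanted, show it only as a sensitivity analysis, state whether it also applies to baseline HV and to HV SDS, and record it in SAP section 3.

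Data queries, and any exclusion for documented measurement error, should follow one symmetric rule for implausibly low and implausibly high HV. Acting on negatives alone would bring the one-sided selection back. At true HV 0, dropping every negative value gives a bias of about 0.80·s, against 0.40·s for the floor.

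The cost is one SAP sentence, one program line and a count per visit. The downside is a few negative minima in the tables.

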### **HV SDSCS**

Individual values for HV SDSCS are calculated using reference values from Table 1 (for boys) or Table 2 (for girls), both given in Appendix D. Each of these tables was derived by tables provided by Prader (1989). For a description of the performed combinations and extensions please refer to the foot note below the attached tables. The abbreviation "CS" in HV SDSCS stands for "cross sectional", meaning that tabled reference values for specific age groups directly correspond to means and standard deviations for HV as observed in the referenced longitudinal study. Averages and variability are estimated for each age group from raw data, not taking into account any information regarding the individual onset or peak of pubertal growth spurt.

### **HV SDSPC**

Individual values for HV SDSPC are calculated using reference values from the tables given in Appendix D. These HV references were obtained for each sex at the end of the referenced longitudinal study, aligning individual velocity curves on mean age of peak height velocity. The abbreviation "PC" in HV SDSPC stands for "peak centered".

Mean time-trends of these four efficacy endpoints will be illustrated graphically.

All four endpoints will be summarized by visit overall and stratified by sex and initially treatment.. In addition, 95% confidence intervals will be calculated for the mean difference between the baseline visit and all later visits, respectively.

#### **4.6.1.1 IGF-1 and IGFBP-3 serum levels**

Blood samples for the determination of IGF-1 and IGFBP-3 serum levels will be drawn at baseline, at 3, 6, 9, 12, 18, and 24 months, then every 6 months during treatment, and at the end of treatment. Serum levels as well as ratios of IGF-1 and IGFBP-3 will be assessed by a central laboratory.

Data regarding secondary efficacy parameters will be summarized by visit overall and stratified by sex and initially treatment. In summary tables by visit overall confidence limit for means will be provided. Time trends of means will be presented graphically for all patients only by sex. In addition, 95% confidence intervals will be calculated for the mean difference between the baseline visit and all later visits, respectively. Relative changes from baseline of IGF-1 and IGFBP-3 will be summarized by visit.

Shift tables for changes in the reference range classification will be provided for IGF-1 and IGFBP-3. Shift tables will be prepared for the two formulations separately. In these tables baseline data will be presented in rows and data from the visits at 6, 12, 18, and 24 months will be cross-tabulated in columns. The categories "low"(< lower limit of normal), "normal", "high" (>upper limit of normal) and "missing" will be used in the shift tables. Shifts between categories will be displayed using absolute counts.

IGF-1, IGFBP-3 and ratio will be expressed in SDS. SDS reflects the deviation of a measured value from the mean value of healthy children of the same sex and chronological age, expressed in units of the standard deviation of unexposed children of the same sex and chronological age.

Standardization of patients' IGF-1, IGFBP-3 and ratio will be performed according to Elmlinger (2004). SDS values will be assessed according to the following formulas:  $SDS = (X1 - X2) / ((X2 - X3) / 2)$  if  $X1 < X2$  and  $SDS = (X1 - X2) / ((X4 - X2) / 2)$  if  $X1 \geq X2$ , where X1 means the measured value, X2 the mean value for the relevant chronological age and sex, X3 the -2 SD value for the relevant chronological age and sex, and X4 the +2 SD value for the relevant chronological age and sex according to Elmlinger (2004).

Mean, -2 SD, and +2 SD values given by Elmlinger (2004) are provided for age intervals. These values were used as references for patients with an age equal to the mid of this age interval. For patients with an age between two mids of age intervals, mean, -2 SD, and +2 SD values will be interpolated.

SDS values of secondary efficacy parameters will be summarized by visit overall and stratified by sex and initially treatment. In summary tables by visit overall confidence limit for means will be provided. Time trends of means will be presented graphically for all patients only. In addition, 95% confidence intervals will be calculated for the mean difference between the baseline visit and all later visits, respectively.

#### **4.6.1.2 Additional efficacy endpoints**

In addition to the endpoints described in 0 and 4.6.1.1, [REDACTED] height age will be derived in the analysis.

For the determination of height age (HA), body height recordings from the baseline and then yearly during treatment period will be compared to mean heights given in the extended reference tables for height (Appendix A). HA will be derived by taking that age from the reference table for which the observed height is the same as the average height in normally growing children.

[REDACTED]

[REDACTED]

[REDACTED]

To assign one height age value to a given height using the respective reference table, the following rule was applied: If the height assessment was between two height assessments in the reference table, the lower age is used, if the height assessment was lower or equal to half of the distance. Otherwise the upper age will be used (i.e. if higher than half of the distance between lower and upper height).

[REDACTED]

[REDACTED], HA and CA will be summarized by visit overall and stratified by sex and initially treatment. In addition 95% confidence intervals will be calculated for the mean difference between baseline visit and all later visits, respectively.

The progresses in CA, [REDACTED] and HA will be compared by deriving the means of the following ratios: [REDACTED]/ΔCA, ΔHA/ΔCA and ΔHA/[REDACTED]. To derive individual ratios corresponding to changes ΔCA, [REDACTED] and ΔHA will be calculated as the difference in CA, [REDACTED] and HA between the baseline visit and the annual visits under treatment. Calculated ratios will be summarized by visit overall and stratified by sex and initial treatment. Performing one-sample t-tests, it will be evaluated whether mean ratios differ significantly from the theoretical value of 1.0.

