#### **4.8 Analyses during an ongoing study**

According to the protocol three interim analyses were planned at the following time points:

- Q4/2011 with data of patients who completed 1 year of treatment
- Q4/2012 with data of patients who completed 2 years of treatment
- Q4/2020 with data of patients who finished treatment

The first two interim analyses were performed as planned including data on 278 treated patients. In the first interim analysis all information regarding the first year of treatment was included that was available on 19-Oct-2011; in the second interim analysis all information regarding the first two years of treatment were summarized based on data cut-off 20-Mar-2013. The third interim analysis was anticipated for Q4 2020 (with data of patients who finished treatment) and to be submitted as per the current RMP version 11 by 2021. However, Sandoz reached out to EMA in Aug-2021 with submitting PAM to provide the study status and ask for final report submission in 2022 EMEA/H/C/000607/MEA/010.3).

This SAP describes the analyses planned for the final analysis that will be performed when all patients have discontinued/completed the study.

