		Females	XX	XX	XX.XX	X.XX	XX.X	XX.X	XX.X	XX.X	XX.X
		Powder	XX	XX	XX.XX	X.XX	XX.X	XX.X	XX.X	XX.X	XX.X
		Solution	XX	XX	XX.XX	X.XX	XX.X	XX.X	XX.X	XX.X	XX.X
		Total	XX	XX	XX.XX	X.XX	XX.X	XX.X	XX.X	XX.X	XX.X

...	Males	XX	XX	XX.XX	X.XX	XX.X	XX.X	XX.X	XX.X	XX.X	XX.X
	Females	XX	XX	XX.XX	X.XX	XX.X	XX.X	XX.X	XX.X	XX.X	XX.X
	Powder	XX	XX	XX.XX	X.XX	XX.X	XX.X	XX.X	XX.X	XX.X	XX.X
	Solution	XX	XX	XX.XX	X.XX	XX.X	XX.X	XX.X	XX.X	XX.X	XX.X
	Total	XX	XX	XX.XX	X.XX	XX.X	XX.X	XX.X	XX.X	XX.X	XX.X

\* Chronological age determined using date of x-ray

[REDACTED]

^ Height age determined using height data from the measurement performed closest to pretreatment x-ray date

[REDACTED]

Programming note: Please add one column 'Status' (value: Completers, Total) before column Visit.

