		Powder	XXX	XXX	X.XX	X.XX	X.X	X.X	X.XX	X.X	X.X	X.X	X.XXXX
		Solution	XXX	XXX	X.XX	X.XX	X.X	X.X	X.XX	X.X	X.X	X.X	X.XXXX
		Total	XXX	XXX	X.XX	X.XX	X.X	X.X	X.XX	X.X	X.X	X.X	X.XXXX
	V09 - V01	Males	XXX	XXX	X.XX	X.XX	X.X	X.X	X.XX	X.X	X.X	X.X	X.XXXX
		Females	XXX	XXX	X.XX	X.XX	X.X	X.X	X.XX	X.X	X.X	X.X	X.XXXX
		Powder	XXX	XXX	X.XX	X.XX	X.X	X.X	X.XX	X.X	X.X	X.X	X.XXXX
		XXX	XXX	X.XX	X.XX	X.X	X.XX	X.X	X.X	X.X	X.X	X.X	XXX
		XXX	XXX	X.XX	X.XX	X.X	X.XX	X.X	X.X	X.X	X.X	X.X	XXX

[REDACTED]; HA - Height Age; CA - Chronological Age  
# two-sided p-value for t-test with null hypothesis that ratio equals 1

Programming note: Please add one column 'Status' (value: Completers, Total) before first column.

TABLE 14.2-3.4 SUMMARY OF OVERWEIGHT PATIENTS BY SEX AND VISIT (FAS)

Sex	Visit	Total	Missing	N	Number of patients (%)	
					Normal	Overweight*
Male	Baseline	XXX	XXX	XXX	XXX (XX.X%)	XXX (XX.X%)
	V02	XXX	XXX	XXX	XXX (XX.X%)	XXX (XX.X%)
	...					
Female	Baseline	XXX	XXX	XXX	XXX (XX.X%)	XXX (XX.X%)
	V02	XXX	XXX	XXX	XXX (XX.X%)	XXX (XX.X%)
	...					
Total	Baseline	XXX	XXX	XXX	XXX (XX.X%)	XXX (XX.X%)
	V02	XXX	XXX	XXX	XXX (XX.X%)	XXX (XX.X%)
	...					

\* Defined by international cut off points for BMI for overweight by sex and age at visit. The cut-off point is defined by the percentile that passes through BMI at 25 kg/m^2 at age 18.

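### The t-test of the mean individual ratio of height-age change to the redacted measure's change against 1.0 is not a valid test of equal progress unless that denominator is essentially error-free

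*SAP*

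**What the plan says.** SAP section 4.6.1.2 (Additional efficacy endpoints) sets out to compare the progress of chronological age (CA), a redacted measure and height age (HA). These "will be compared by deriving the means of the following ratios": redacted measure over CA, HA over CA, and HA over redacted measure. Each ratio uses a child's changes "between the baseline visit and the annual visits under treatment". One-sample t-tests follow, by which "it will be evaluated whether mean ratios differ significantly from the theoretical value of 1.0". The footnote to Table 14.2-3.3 specifies a "two-sided p-value for t-test with null hypothesis that ratio equals 1".

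The definition of the third measure is blacked out. Readable text around it points to a radiograph:
- A footnote to Table 14.2-3.1 reads "Chronological age determined using date of x-ray", and another takes the baseline height nearest the pre-treatment film.
- Protocol 7.1.1 records a historical left hand and wrist X-ray.
- Protocol 7.3.3 mentions bone age beside chronological age.
- The SAP literature list includes a hand-and-wrist skeletal atlas and a skeletal-maturity method.

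No readable text gives a reading error for the measure or a rule for small, zero or negative denominators.

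**The concern.** The mean of individual ratios is not the ratio of the means. If two quantities have the same true change and the one in the denominator is measured with independent error, the average of the individual ratios lies above 1. The t-test then addresses whether the mean ratio is 1, which is not the same as whether the two measures progressed equally. Denominators near zero add a second problem: a few extreme ratios can dominate the mean and SD.

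These ratio tests are the only significance tests in the readable SAP; the rest is descriptive summaries and confidence intervals. A small p-value here will therefore attract attention, and for this ratio it may reflect measurement error in the denominator rather than a difference in progress.

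**Working it through.** **Inputs from the documents.** One-sample t-test, null value 1, two-sided, at annual visits. Alpha is not stated; 5% is assumed, in line with "95% confidence intervals will be calculated for the mean difference between baseline visit and all later visits". The upper bound on N comes from SAP 4.8 ("including data on 278 treated patients"); the number with a valid ratio at each visit is not given.

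**Assumed, because the documents give nothing.** Reading-error SD s = 0.15 to 0.5 year per film; true change 1.2 per year of follow-up with between-child SD 0.25 per year (floored at 0.3 per year); error SD of 0.1 year in HA change; N = 250.

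**Step 1: the plan's figure of 1.0.** The SAP shows no derivation. With an error-free denominator, as is nearly true of change in CA, simulation gives a mean ratio of 1.000 and about 2.5% rejections on each side. The null value therefore suits those two ratios as far as this problem goes.

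**Step 2: noisy denominator.** For X/Y with equal means, to first order:

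E[X/Y] ≈ 1 + CVy² − ρ·CVx·CVy

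This equals 1 only if CVy = 0 or CVy = ρ·CVx. For a common true change T and independent error of SD σ in the denominator change, it becomes 1 + σ²/T².

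| T (years) | σ (years) | First-order mean | Simulated mean (n = 200) | Upward rejection |
|---|---|---|---|---|
| 1 | 0.2 | 1 + 0.04/1 = 1.040 | 1.045 | 69% |
| 2 | 0.3 | 1 + 0.09/4 = 1.0225 | 1.024 | 49% |
| 6 | 0.3 | 1 + 0.09/36 = 1.0025 | 1.002 | 9% |

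A small bias matters because the standard error is also small. In the first row it is about √(0.1² + 0.2²)/√200 = 0.224/14.14 = 0.016, so a bias of 0.040 is about 2.5 standard errors.

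**Step 3: main simulation.** X = T + N(0, 0.1) and Y = T + N(0, s√2), with T identical in X and Y for each child. The error SD of the denominator change thus runs from 0.15 × √2 = 0.21 to 0.5 × √2 = 0.71 year. Upward rejections in 2,000 trials per setting, N = 250:

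| Follow-up | s = 0.15 | s = 0.25 | s = 0.35 | s = 0.5 |
|---|---|---|---|---|
| Year 1 | 70% | 60% | 25% | 4% |
| Year 2 | 27% | 63% | 81% | 59% |
| Year 4 | 11% | 22% | 38% | 66% |
| Year 6 | 5% | 12% | 18% | 35% |

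Repeat runs move these by a few points: the lowest year-2 figure ranges from 23% to 27%, and the year-6 figures span 5% to 36%. Downward rejections never exceed 1%. At year 1 the typical mean ratio is 1.04, 1.14, 1.21 and 1.17 across the four values of s.

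**Step 4: very large error.** At year 1, denominators of 0.1 year or less occur in 0.04%, 0.6%, 2.4% and 7.1% of children across the four values of s. Once they are common, extreme ratios inflate the SD and rejections vanish. A handling rule then decides the result: with T = 1 year, σ = 0.6 and n = 200, upward rejection is 3.3% if all ratios are kept and 98.5% if denominators of 0.1 year or less are dropped.

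**Step 5: a case that reverses.** Let mean progress be equal, with true progress differing between children: CVx = 0.30, CVy = 0.15, ρ = 0.8. The formula gives 1 + 0.0225 − 0.036 = 0.9865. Simulation at n = 200 gives 0.987, with 16% downward and 0.2% upward rejections. At ρ = 0.5 the terms cancel (0.0225 − 0.0225) and the bias is about 0.

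**Step 6: alternatives.** On the Step 3 data, a paired t-test of X − Y against 0 rejects in about 4–6% of trials, both sides together. A log ratio does not fully repair the problem: with T = 1 year, σ = 0.2 and n = 200 it still rejects upward in 15.7%.

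**The case against.** The strongest reply is that the denominator is blacked out. The readable X-ray footnotes concern CA and the height chosen for HA, so reading the measure as a radiographic age is an inference, though a well-supported one. Hidden paragraphs may contain a rule for small or non-positive changes. A missing rule therefore cannot be charged to the plan.

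The test also matches its written null, a mean ratio of 1. That is true, but section 4.6.1.2 introduces the ratios as its way of comparing progress, and for that purpose 1.0 is the wrong reference when the denominator is noisy.

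A reader might infer that the plan will yield falsely favourable p-values. The documents do not support that. No passage calls a ratio above 1 favourable, the p-value is two-sided, and both the size and direction of the bias rest on assumed inputs. Protocol 1.2.3 does report faster bone maturation under growth hormone, which makes a favourable reading easy to slip into, but the SAP does not make it.

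Two partial safeguards exist. Table 14.2-3.2 is titled to give mean changes with 95% CIs for the redacted measure and HA, and Table 14.2-3.3 shows medians, quartiles and extremes. Neither supplies a paired comparison with a CI, and neither makes the planned p-value valid.

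The low-impact argument stands in full. HA is not among the endpoints in SAP 2.3, and the study is single-arm and largely descriptive.

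**Conclusion.** The concern holds in a limited form. For the ratio of HA change to the redacted measure's change, the t-test against 1.0 is not a valid test of equal progress unless the denominator is essentially error-free and does not vary independently of the numerator. If the measure is read from a radiograph, the mean ratio under equal true progress is generally above 1. Upward rejection is then well over the nominal 2.5% in most of the settings examined, chiefly in the first two years when reading error is moderate. The percentages illustrate assumed error sizes and N = 250; they are not estimates for this trial. Severity is low: one of three ratios, in an additional efficacy endpoint, with nothing in the primary diabetes analysis depending on it.

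**What to change.** In SAP 4.6.1.2 and Table 14.2-3.3, for this ratio only:
- Replace the p-value with the paired difference, change in HA minus change in the redacted measure, in years, tested against 0 with a 95% CI.
- If a ratio is wanted, show the ratio of mean changes with a Fieller or bootstrap CI.
- Keep individual ratios as median and quartiles without a p-value. If the blacked-out text has no rule for small or non-positive denominators, add one.

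The two ratios over CA need no change on this account. The cost is about one sentence in the SAP and a small programming change on the same data. The drawback is that the result is in years rather than as a unit-free ratio.
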